4.2. Sample Size and Power Considerations

Assuming a difference of 1.6 in the mean MMDs between the two arms, and a common standard deviation (SD) of 5.8, 474 participants are required for the study (237 per arm) to ensure 85% power and using a two-sided alpha of 5%. Sample size was calculated using a two-sample *t*-test assuming equal variance. Assuming 15% drop out, at least 558 participants will be randomized in a 1:1 ratio to CT-132 or digital control.

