8.5.5. Change in the number of headaches with at least moderate severity from baseline (28-day run-in period) to Week 12 (previous 28 days, Week 9 through Week 12)

This endpoint will be performed on the mITT analysis set, in addition to the ITT analysis set.

Each recorded headache's severity will be scored in the following manner:

- None = 0
- Mild = 1
- Moderate = 2
- Severe = 3

Headaches that started at one period and ended in the following period will be assigned to the period in which the headache started.

The change from run-in will be calculated as (Weeks 9-12 number of headaches with at least moderate severity – run-in number of headaches with at least moderate severity).

An ANCOVA model will be used to analyze this endpoint. The dependent variable is the change in number of headaches with at least moderate severity from run-in period to Week 9-12 for each participant.

The model will adjust for the following covariates: treatment arm and number of headaches with at least moderate severity at run-in period

This analysis will use observed data only.

8.5.6. Change from baseline in the Migraine-Specific Quality-of-Life Questionnaire v2.1 (MSQ) total score at Week 12

The MSQ is a 14-item questionnaire that is completed at baseline, Week 4, Week 8, and Week 12. Each item consists of 6 possible responses, scored 1 to 6. Higher scores represent more severe migraines.

For the purpose of calculating the MSQ total score, the responses to the 14 items will be reverescoded (scores 1,2,3,4,5,6 will be converted to 6,5,4,3,2,1 respectively)

For each visit, the MSQ score (after reverse-coding) will be calculated as:

Total score = ([sum of the 14 reversed item scores - 14] / 70) * 100

In case of missing items, the MSQ score for the visit will be considered missing.

An ANCOVA model will be used to analyze this endpoint. The dependent variable is the change from baseline in MSQ to week 12 for each participant.

The model will adjust for the following covariates: treatment arm and baseline MSQ.

This analysis will use observed data only.

8.5.7. Change from baseline in the Migraine-Specific Quality-of-Life Questionnaire v2.1 (MSQ) total score at Week 8

This endpoint will be analyzed in the same manner as described in Section 8.5.6, using the Week 8 assessment.

8.5.8. Change from baseline in the Migraine-Specific Quality-of-Life Questionnaire v2.1 (MSQ) total score at Week 4

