This endpoint will be analyzed in the same manner as described in Section 8.5.6, using the Week 4 assessment.

8.5.9. Change from baseline (28-day run-in period) in the Migraine Disability Assessment (MIDAS) to Week 12

The MIDAS questionnaire assesses the impact the migraine has on the participant's life. It consists of 5 questions regarding the number of days impacted. In addition, there are two questions for physician use. The endpoint will use only the first 5 questions. The MIDAS score for a visit is the sum of responses of the first 5 questions. In case of missing items, the MIDAS score for the visit will be considered missing.

This endpoint will be analyzed using Wilcoxon rank-sum test.

This analysis will use observed data only.

8.5.10. Change from baseline (28-day run-in) period to Week 12 (previous 28 days, Week 9 through Week 12) in the number of migraines with use of an acute medication

This endpoint will be performed on the mITT analysis set, in addition to the ITT analysis set.

The number of migraines with use of an acute medication will be counted for the run-in period and for post randomization period.

The change from baseline will be calculated as number of migraines in weeks 9-12 minus number of migraines in the run-in period with use of an acute medication.

Migraines that started at one period and ended in the following period will be assigned to the period in which the migraine started.

An Analysis of Covariance (ANCOVA) model will be used to analyse this endpoint. The dependent variable is the change from baseline to Week 12 in the number of migraines with use of an acute medication each participant.

The model will adjust for the following covariates: treatment arm, baseline number of migraines with use of an acute medication. The analysis will use only observed data.

8.5.11. Change in the number of MHDs from baseline (28-day run-in) to Week 12 (previous 28 days, week 9 through Week 12)

This endpoint will be calculated and analyzed as described in Section 8.1.3, using MHDs instead of MMDs.

[figure not shown]
This endpoint will be performed on the mITT analysis set, in addition to the ITT analysis set.

[figure not shown]

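### The Week 12 MSQ analysis discards Week 4 and Week 8 scores from participants with no Week 12 score; a repeated-measures model would use them at little cost (minor)

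*SAP*

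**What the plan says.** SAP 8.5.6 states that the MSQ is "completed at baseline, Week 4, Week 8, and Week 12". For Week 12, "The dependent variable is the change from baseline in MSQ to week 12 for each participant". On covariates: "The model will adjust for the following covariates: treatment arm and baseline MSQ". On missing data: "This analysis will use observed data only". A partly completed form is also lost: "In case of missing items, the MSQ score for the visit will be considered missing".

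The other two visits get their own models. SAP 8.5.7: "This endpoint will be analyzed in the same manner as described in Section 8.5.6, using the Week 8 assessment". SAP 8.5.8: "This endpoint will be analyzed in the same manner as described in Section 8.5.6, using the Week 4 assessment".

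Related rules elsewhere:

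- SAP 6.1 keeps early-termination measurements in listings and out of analyses, although the protocol schedule (1.2) collects MSQ at the combined Week 12/ET visit.
- SAP 8.5 places secondary analyses on the ITT set unless stated otherwise.
- SAP 4.2 plans for loss: "Assuming 15% drop out, at least 558 participants will be randomized".
- Protocol 9.4.4 handles missing data for the primary endpoint by multiple imputation under MAR. SAP 8.5.2 to 8.5.4 reuse the 100 completed datasets for MMD secondaries, and 8.5.11 applies the same method to MHDs.
- Protocol 9.4.5 also names ANCOVA for MSQ.
- SAP 8.6 makes secondary p-values and intervals nominal and excludes them from inference.

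The visible text gives no imputation, repeated-measures or sensitivity analysis for MSQ. MMRM appears only in the protocol's abbreviation list.

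**The concern.** A complete-case ANCOVA on arm and baseline MSQ rests on missingness at Week 12 being unrelated to outcome once arm and baseline are known. Someone whose quality of life is poor at Week 4 or 8 may be more likely to leave. Those scores predict both leaving and the unseen Week 12 value, and the planned model cannot use them.

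If this happens differently in the two arms, the participants left at Week 12 are selected differently, and the arm difference shifts. A likelihood-based repeated-measures model also allows missingness to depend on the observed Week 4 and Week 8 scores. At stake is how far the reported Week 12 MSQ difference and its interval can be trusted. The trial's success criterion is not at stake.

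**Working it through.** **Scale of the loss.** The plan's own sample size reproduces. With difference 1.6, SD 5.8, two-sided 5% and 85% power, the normal approximation gives 2 × (5.8/1.6)² × (1.960 + 1.036)² ≈ 236 per arm. The exact t-test gives 237, so 474 in total. 474/0.85 = 557.6, rounded up to 558. The planned loss is 558 − 474 = 84 participants who could be absent from the Week 12 MSQ model, before counting incomplete forms.

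**Why the arms must differ.** Let d be the dropout fraction in an arm and m the mean Week 12 residual (after adjustment for baseline) of those who leave, relative to the whole arm. Those who remain then have mean residual −d·m/(1 − d). Ignoring re-estimation of the baseline slope among those remaining, the bias in the difference is about

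−[d₁m₁/(1 − d₁) − d₀m₀/(1 − d₀)], with 1 = CT-132 and 0 = control.

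With equal d and equal m the two terms cancel, so dropout after poor early MSQ does not by itself bias the contrast.

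**Simulations.** The documents give no MSQ SD, correlation or effect. All settings below assume SD 20, compare the planned ANCOVA with a maximum-likelihood model using all visits, and let dropout depend only on observed MSQ.

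- Setting A: 279 per arm, 15% lost, all after Week 8, correlations 0.6 to 0.8, true difference 4, 1,000 trials.
- Setting B: 279 per arm, losses after Week 4 or Week 8, correlation 0.5 or 0.7, true difference 0 or 5, 1,500 trials.
- Setting C: average dropout 15%, correlation 0.5 to 0.7.

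Results for setting B (positive bias favours CT-132; rates are control vs CT-132):

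| Dropout pattern | ANCOVA bias | All-visits bias | ANCOVA rejection, no true effect |
|---|---|---|---|
| 15% each, unrelated to MSQ | about 0 | about 0 | 5–6% |
| 15% each, same dependence | within 0.03 | within 0.04 | 4–5% |
| 10% vs 20%, same dependence | +0.6 | within 0.07 | about 8% |
| 15% vs 30%, same dependence | +0.8 to +1.0 | within 0.06 | 8–10% |
| 15% each, dependence in CT-132 only | +0.9 to +1.0 | within 0.09 | 8–11% |
| 15% each, opposite dependence (extreme) | +1.7 to +2.0 | within 0.04 | 23–26% |

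**Check against the formula.** For 10% vs 20%, the multiplier is 0.20/0.80 − 0.10/0.90 = 0.139, so a bias of 0.6 needs m = −0.6/0.139 ≈ −4.3 points. For dependence in one arm, the multiplier is 0.15/0.85 = 0.176, so 0.9 to 1.0 needs m of about −5.1 to −5.7. Leavers who would have scored roughly 4 to 6 points (0.2 to 0.3 SD) below their arm's average are enough.

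**Range across settings.**

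- Same mechanism in both arms: −0.1 to −0.2 in A, near zero in B and C.
- Rate or dependence differing by arm: 0.6 to 1.0 in B, 0.4 to 0.7 in C. Overall 0.4 to 1.0 point, or 0.02 to 0.05 SD.
- Opposite mechanisms: 1.1 to 1.2 in C, 1.7 to 2.0 in B, 1.9 to 2.9 in A. The sign depends on which arm loses which participants.
- Variance with all visits: 2 to 4% lower in A, roughly 0 to 7% lower in C. One example from B, at correlation 0.7 with dropout unrelated to MSQ: (1.281/1.307)² = 0.961, about 4% lower.

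**The case against.** **Nothing decisive depends on MSQ.** Study success rests on MMDs alone, and SAP 8.6 makes secondary p-values and intervals nominal. This stands and keeps the point minor. It does not remove the bias: the estimate will still be reported and read.

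**The ordinary case is close to nil.** This stands too. A reader might infer that dropout following poor early MSQ is enough to bias the comparison. It is not; the mechanism or rate must differ between arms. A reader might also take the extreme setting, where bias of 1.9 to 2.9 points is 48 to 73% of the assumed 4-point effect, as the expected size. Nothing in the documents suggests that control participants leave when worse while CT-132 participants leave when better. That setting also places every loss after Week 8, which suits the all-visits model best. A participant lost before Week 4 gives that model no post-baseline MSQ.

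**The alternative also has an assumption.** It is valid under MAR given observed MSQ; under MNAR both methods can be biased. A reader might infer that this is the same MAR assumption the primary analysis makes. That cannot be verified, because the imputation detail of SAP 6.3 is not visible in the public text. The missing text does not affect the MSQ reading, since 8.5.6 sets its own observed-data rule.

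**Earlier scores are not wasted altogether.** They enter the Week 4 and Week 8 analyses, and protocol 7.2 asks that those who stop using the app ideally be observed to the end. So it would be loose to say that MSQ covers study completers only. What holds is that the Week 12 estimate ignores them.

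**Conclusion.** The point holds as a minor, inexpensive improvement. The Week 12 MSQ model leaves out Week 4 and Week 8 scores from anyone without a Week 12 score. Where dropout depends on earlier MSQ and differs between arms in rate or dependence, the Week 12 difference is biased by about 0.4 to 1.0 point in moderate cases, and by about 1 to 3 points only with opposite mechanisms in the two arms. Where dropout works alike, bias is about 0 to 0.2 points and the benefit is a few percent of variance.

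These sizes rest on an assumed SD of 20 and correlation of 0.5 to 0.7 (0.6 to 0.8 for the upper end of the extreme range), and they scale with the SD. The documents neither show nor predict differential dropout, so they support a statement that the estimate can be biased, not that it will be. The primary result and the study's success criterion are untouched.

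**What to change.** Replace the three ANCOVAs in SAP 8.5.6 to 8.5.8 with one repeated-measures model on change in MSQ at Weeks 4, 8 and 12. Include arm, visit, arm-by-visit, baseline MSQ and baseline MSQ-by-visit, with an unstructured covariance. Report the arm contrast at each visit. Keep the observed-data ANCOVA as a sensitivity analysis. Adding baseline preventive use as a covariate is optional. Multiple imputation that uses the earlier MSQ scores would also meet the point.

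The data are already collected, so there is no added participant burden. The costs are SAP wording, standard code, a covariance structure to specify, and a recorded departure from protocol 9.4.5. SAP section 1 already provides for this: the SAP prevails, and differences are to be described in the statistical report and at the end of the SAP.

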8.6. Multiplicity Control

No multiplicity adjustment will be made to secondary endpoints, sensitivity analyses, and subgroups. *P*-value and confidence interval for secondary endpoints not controlled for multiplicity and exploratory endpoints will be nominal and will not be used for statistical inference.

8.7. Exploratory Endpoints

All exploratory analyses will be conducted on the ITT analysis set.

8.7.13. Proportion of participants who have at least a 50% reduction from baseline (28-day run-in period) in the number of MHDs at Week 12 (previous 28 days, Week 9 through Week 12)

This endpoint will be calculated and analyzed as described in Section 8.5.1, using MHDs instead of MMDs.

8.7.14. Change from baseline (28-day run-in period) in the mean number of MHDs over 12 weeks.

This endpoint will be calculated and analyzed as described in Section 8.5.4, using MHDs instead of MMDs.

8.7.15. Change from baseline (28-day run-in period) in the number of MHDs recorded over the previous 28 days at Week 4

This endpoint will be calculated and analyzed as described in Section 8.5.2, using MHDs instead of MMDs.

8.7.16. Change from baseline (28-day run-in) in the number of MHDs recorded over the previous 28 days at Week 8

This endpoint will be calculated and analyzed as described in Section 8.5.3, using MHDs instead of MMDs.

8.8. Patient Global Impression of Change (PGI-C) score at Week 12

The Patient Global Impression of Change (PGI-C) is a self-reported, 7-point scale depicting a patient's rating of overall improvement.

The PGI-C will be measured at Week 12.

T-test will be used to analyze this endpoint.

8.8.1. Shift from High Frequency Episodic Migraine (HFEM) at baseline (28-day runin period) to Very Low Frequency Episodic Migraine (VLFEM) or Low Frequency Episodic Migraine (LFEM) at Week 12 (previous 28 days, Week 9 through Week 12)

During the 28-day run-in period each participant will be classified as having High Frequency Episodic Migraine (HFEM; 8-14 MMDs) or Low Frequency Episodic Migraine (LFEM; 4-7 MMDs).

During weeks 9-12, participants will be classified as HFEM, LFEM or Very Low Frequency Episodic Migraine (VLFEM; < 4 MMDs). Note that per inclusion criteria at baseline there are no VLFEM participants.

A shift table will be presented including the number and percentage of participants shifting from each category at run-in period to each category at Weeks 9-12, by treatment group.

This analysis will include only subjects with at least 10 days of reporting during Week 9-12, and number of migraines will be prorated as described in Section 6.3. Patients with less than 10 days of reports will be considered missing in this analysis.

9. SAFETY ANALYSIS

All safety analyses will be conducted on the safety analysis set and will be descriptive.

AE will be recorded from date of signing the ICF and onwards. All AEs will be coded by system organ class (SOC) and preferred term (PT) using Medical Dictionary for Regulatory Activities (MedDRA) version 25.1.

Summaries will present non-treatment emergent AEs (AEs started before first day of treatment) and treatment-emergent AEs (TEAE; AEs started after first day of treatment) separately.

In an overview table, the number and percentage of participants who experienced a TEAE, non-TEAE, serious TEAE, treatment related TEAE, died due to an AE, or discontinued from study treatment due to a TEAE will be summarized by treatment.

The percentages of participants with TEAEs will be summarized by treatment using MedDRA preferred term nested within system organ class (SOC). Events will be ordered by decreasing frequency within SOC, and SOC with be ordered by decreasing frequency.

Similar summary will be presented for non-TEAE, serious TEAE, treatment related TEAE and TEAE related to worsening of migraine.

AEs with missing start date will be considered as a TEAE.

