#### 8.4.1. Time Period and Frequency for Collecting AE and SAE Information

All AEs and SAEs will be collected from the signing of the informed consent form (ICF) until the follow-up visit at the time points specified in the SoA (Section 1.2).

AEs will be divided into non-treatment-emergent AEs (non-TEAEs) and treatment-emergent AEs (TEAE). Non-TEAEs are those AEs that occurred prior to the first study treatment and TEAEs are those AEs with onset date/time at or after the first study treatment.

All SAEs will be recorded and reported to the sponsor or designee immediately and under no circumstance should this exceed 24 hours, as indicated in Appendix 3. The investigator will submit any updated SAE data to the sponsor within 24 hours of it being available.

Investigators are not obligated to actively seek information on AEs or SAEs after conclusion of the study participation. However, if the investigator learns of any SAE, including a death, at any time after a participant has been discharged from the study, and he/she considers the event to be reasonably related to the study intervention or study participation, the investigator must promptly notify the sponsor.

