1. INTRODUCTION

This Statistical Analysis Plan (SAP) describes the planned analysis for Click Therapeutics study CT-132-R-001, "A Randomized Double-blind, Digital-Controlled, Parallel-Group, Virtual Study to Evaluate the Effectiveness and Safety of a Digital Therapeutic (CT-132) as Adjunctive Therapy in Late Adolescents and Adults for the Prevention of Episodic Migraine". This SAP should be read together with the protocol for full details on the study.

The SAP is intended to agree with the protocol with regard to statistical aspects that were specified in the protocol. However, the SAP may contain additional details for analyses that were defined in the protocol, and may provide details on statistical aspects that were not described in the protocol. In case of disagreement between the SAP and the protocol, the SAP prevails. Differences will be described in the statistical report and at the end of this document.

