7.3. Medical History and Medications

The medical history and medication analysis will be performed using the ITT analysis set.

Medical history will be summarized and presented by treatment group.

The proportion of participants who received previous therapy will be summarized by WHOdrug preferred term and presented by treatment group. A separate summary will be presented for migraine medications taken prior to the study.

The proportion of patients who report concomitant medications during study treatment will be summarized by WHOdrug preferred term and presented by treatment group regardless of whether the medication was taken prior to baseline.

Previous therapy is defined as medication with end date earlier than the baseline date (study app activation).

Concomitant medication is defined as medication with an end date on or later than the baseline date (study app activation) or missing end date.

The proportion of participants who use acute migraine medication and preventive migraine medication will be summarized, separately, by WHOdrug preferred term and presented by treatment group.

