7.6. Exposure

Exposure to study intervention, in days, will be calculated for each participant as number of days from first day of treatment until last day of treatment + 1. First day of treatment is defined as the first date with adherence to task and last day of treatment is defined as the last date of adherent to task.

Exposure will be summarized using descriptive statistics by treatment group.

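### SAP 9 places an AE with known onset on the first day of treatment in neither the TEAE nor the non-TEAE category, although Protocol 8.4.1 includes that boundary

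*SAP*

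**What the plan says.** SAP 9 states that the safety summaries will present "non-treatment emergent AEs (AEs started before first day of treatment) and treatment-emergent AEs (TEAE; AEs started after first day of treatment) separately". Its one supplementary rule is that an AE with no start date counts as a TEAE.

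SAP 9 does not itself say which day is the first day of treatment. SAP 7.6, written for exposure, does: "First day of treatment is defined as the first date with adherence to task". That makes it a calendar date. SAP 6.1 numbers study days from the baseline visit, with the baseline day as Day 0 and the treatment period starting at Day 1.

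Protocol 8.4.1 treats onsets before first study treatment as non-TEAEs and continues: "TEAEs are those AEs with onset date/time at or after the first study treatment".

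On how the two documents relate, SAP 1 says: "The SAP is intended to agree with the protocol with regard to statistical aspects that were specified in the protocol". It adds: "In case of disagreement between the SAP and the protocol, the SAP prevails". It also says: "Differences will be described in the statistical report and at the end of this document".

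For medications, SAP 7.3 draws a comparable line with no gap: "Previous therapy is defined as medication with end date earlier than the baseline date", and "Concomitant medication is defined as medication with an end date on or later than the baseline date". A missing end date is also assigned, to concomitant. The anchor there is app activation rather than the first task.

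**The concern.** A TEAE definition should give every dated AE one category. Two strict inequalities around the same date leave that date unassigned, and the missing-date rule does not help because the onset is known. The result is odd: an undated AE is a TEAE, while one known to have begun on the day the participant first used the intervention is not.

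AE frequency and severity, discontinuation due to AEs, and AEs related to worsening of migraine are the safety endpoints (Protocol 3, SAP 3.4). Protocol 2.3.1 names temporary worsening of migraine as the main potential risk. SAP 9 reports these mostly through TEAE status, so a first-day onset would be missing from the TEAE, non-TEAE, serious TEAE, treatment-related TEAE, migraine-worsening TEAE and discontinuation-due-to-TEAE summaries. Someone who tries the app once, has an AE that day and stops because of it is the clearest example.

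**Working it through.** The plan gives no figure to reproduce. The check applies each rule to every possible onset.

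**Classification.** Let d = onset date minus first day of treatment, in days.

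- SAP 9: non-TEAE if d < 0; TEAE if d > 0.
- Protocol 8.4.1, applied to dates: non-TEAE if d < 0; TEAE if d ≥ 0.

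| d | SAP 9 | Protocol 8.4.1 |
|---|---|---|
| -2 | non-TEAE | non-TEAE |
| -1 | non-TEAE | non-TEAE |
| 0 | neither | TEAE |
| +1 | TEAE | TEAE |
| +2 | TEAE | TEAE |

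The only unclassified case is d = 0.

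**Dates and times.** The protocol's rule works on date and time. If times are available, a first-day AE that began before first use is a non-TEAE under the protocol, and one at or after first use is a TEAE. Either way the protocol classifies it and SAP 9 does not.

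**Choice of anchor.** If the first day of treatment is the first task date (SAP 7.6), that date is lost. If it is Day 0 (SAP 6.1), Day 0 is lost. The anchor changes which date is affected, not whether one is.

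**Size in time.** The intervention lasts 12 weeks: 12 × 7 = 84 days. One date is 1/84 = 0.012, about 1.2% of planned treatment days.

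**Extreme case.** Take a participant with tasks on one date only. Under SAP 7.6, exposure = (last day − first day) + 1 = 0 + 1 = 1 day. One completed task puts this person in the safety set (SAP 5.6). Exposure days on which a known onset can be a TEAE: 0 under SAP 9, 1 under the protocol at date level. Onsets after that date can still be TEAEs, because AE collection runs to the follow-up visit.

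**Effect on counts.** A participant whose only AE starts on the first day counts as having an AE but is in neither the TEAE nor the non-TEAE row. The two rows need not sum to the all-AE participant count anyway, since one person can be in both, so this loss would not show up as a failed total.

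**The case against.** The strongest reply is that the events are not lost. Protocol 9.4.8 says without condition that counts of AEs, SAEs, related AEs, related SAEs, AEs leading to study discontinuation and AEs leading to death will be presented. None of these depends on TEAE status, the visible SAP does not withdraw them, and the SAP is to be read together with the protocol. The death row in the SAP 9 overview is not restricted to TEAEs either. This stands, and it rules out the stronger inference that first-day events vanish from safety reporting. What is lost is the TEAE classification and the summaries built on it. Migraine worsening is the one listed summary with no unsplit counterpart in Protocol 9.4.8.

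A second reply is that SAP 9 is silent about the first day, so the protocol fills the gap and the precedence clause is not triggered. The SAP's stated aim of agreeing with the protocol supports that reading. But 'after' the first day excludes that day, so a programmer following SAP 9 has no warrant to include it, and two programmers could reasonably differ.

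Third, the wording sits in parentheses in a sentence about table layout and is probably shorthand for on or after. That is likely, but it explains the gap without closing it.

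Fourth, Appendix A, the table shells and the announced list of differences from the protocol cannot be seen. A reader might infer that the outputs will be wrong, or that this is an undeclared departure from the protocol. The documents support neither inference.

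**Conclusion.** The point holds for the rule as written. SAP 9 leaves a known first-day onset unclassified, Protocol 8.4.1 does not, and the precedence clause means that the protocol text does not automatically repair the SAP.

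Its reach is limited: one calendar date per participant, and the whole exposure only for a one-day user. The documents give no basis for estimating how many AEs start on that date, and it may be few. Safety analyses are descriptive, and neither the primary analysis nor its success criterion is affected.

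The conclusion assumes only that 'before' and 'after' carry their ordinary meaning. It is a drafting defect in a safety definition that should be corrected, not evidence of under-reporting.

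**What to change.** Reword the sentence in SAP 9 to follow Protocol 8.4.1: a TEAE is an AE with onset at or after first study treatment, and a non-TEAE is an AE with onset before it. Add one rule: if onset is on the first day of treatment and no usable time places it relative to first use, count it as a TEAE. This goes in the same direction as the SAP's existing rule for missing start dates. SAP 9 should also state which date is the first day of treatment, for example by referring to SAP 7.6.

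Every AE with a known onset date then has exactly one category. Partial start dates are not covered explicitly by SAP 9 or by this change and would need their own line.

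The cost is one reworded sentence and one added rule. The small downside is that a few first-day events that began before first use may be counted as TEAEs.
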